**Protocol**

**Proposal Summary**

This proposal aims to investigate the effect of a promising treatment for persistent post Traumatic Brain Injury (TBI) symptoms, and to monitor TBI patient's recovery by an objective technique along with standard clinical assessments. The treatment tool is the application of repetitive Transcranial Magnetic Stimulation (rTMS) [1] to the dorsolateral prefrontal cortex (DLPFC) of the brain. The treatment efficacy and monitoring TBI patients' recovery will be objectively assessed using Electrovestibulography (EVestG™) [2]; this will be in parallel with clinical and standard assessments. This proposal is built upon our encouraging pilot studies (*REB# B2011:116 and REB# B2012:076*)

TBI is a significant health problem mainly because of its plausible prolonged sequelae and lack of objective measures for recovery. The conventional treatment after a TBI is physical rehabilitation that helps with motor functional recovery. However, there are usually some disabling persistent post-TBI symptoms (mostly neurological) that do not respond to the current clinical and physical rehabilitation. rTMS, on the other hand, is a promising, well-tolerated, non-invasive brain neuromodulation technique that has emerged as a therapeutic tool for a variety of neurological conditions. Thus, we aim to investigate the effect of rTMS treatment on post-TBI symptoms in patients identified by our medical collaborators (Drs. [name] and [name]). Equally important is to have an objective measure of treatment efficacy and patient's symptoms recovery. EVestG™ [2] is a noninvasive technique to record neural activity from the vestibular apparatus and vestibular nuclei in the external ear. After a head injury, people commonly experience balance (vestibular) problems and dizziness, as well as confused thinking. Considering the well-known bidirectional anatomical links of the vestibular system, following an impact TBI, EVestG signals are expected to change, and our pilot studies show a great potential of EVestG to monitor the impact of TBI. Thus, we aim to use EVestG as an objective measure to monitor the recovery path during and after the rTMS treatment in parallel to clinical and neuro-psychological assessments.

The proposed research has the potential to lead to a treatment and objective monitoring protocol that would provide a much faster, more economical and more efficient treatment method than the current techniques. The outcomes of this proposal will provide a reliable means for quick and accurate diagnosis and treatment of TBI as well as monitoring its progress towards recovery.

## Introduction

### a. Rationale

Traumatic brain Injury (TBI) occurs when a sudden trauma causes either transient or permanent brain damage. In some literature, the term “concussion” is used to refer to the most common (mild) type of TBI. It is defined as an immediate and transient impairment of neural functions, such as the alteration of consciousness, balance and/or visual disturbances, due to a direct blow to the head or after a blow elsewhere that is transmitted to the head. In other literature, mostly neurological journals (and in this proposal), mild TBI (mTBI) and concussion are used interchangeably.

Every three minutes, there is a TBI case in Canada [3], and 50,000 Canadians sustain brain injuries each year [4]. Motor vehicle crashes and traffic-related incidents are major causes of TBI; 40% of TBI cases in Manitoba are due to car accidents [5]. Transport Canada reports that the road accident rate of the province of Manitoba is greater than the national average [6]. According to MPI’s 2011/12 annual report, there was an 89% increase in brain injury claims from 146 in 2010/11 to 276 in 2011/12 [5].

The majority of patients with mTBI recover in the first 2-4 weeks; the recovery time is much longer (a few years) for those with severe TBI. In general, the fastest improvement occurs in the first six months after injury and the patient may continue to get better over a period of up to two years. However, many survivors of severe TBI and mTBI continue to experience disabling persistent post-TBI symptoms including somatic and emotional symptoms (sleep disturbances, fatigue, headache and emotional changeability) [7], as well as cognitive [8,9], visual [10-15], and vestibular abnormalities [16,17]. Any of these adverse consequences of TBI impact the individual's quality of life and functionality for years after the injury. In fact, half of the hospitalized TBI patients develop TBI-related long-term or permanent disability [18], and over 70% of people diagnosed with severe TBI require long-lasting care and support [19]. In addition, TBI is strongly associated with subsequent disabling neurological disorders including Alzheimer's and Parkinson's diseases [20].

TBI also imposes a heavy cost on the healthcare systems. The direct medical cost per TBI patient in need of rehabilitation in Canada is estimated to be as high as \$93,340 per year (in 2007 CAD) [21]. In Australia, which has a similar economy and healthcare system to Canada, an average lifetime cost of severe TBI is AU\$4.8 million per patient [22]. The estimated annual total medical cost of TBI cases for the United States is \$79.1 billion (in 2013 USD) [23].

Given that TBI imposes substantial medical and socio-economic burden on patients, the healthcare system and the society in Canada and worldwide [18,24], there is an urgent need to develop effective assessment and treatment interventions for TBI and objective quantitative techniques for monitoring the recovery of patients. The two main technologies (rTMS and EVestG) proposed to be used in this study have already shown the potential to be used as

---

 The rates of concussion usually include the minor to moderate head injuries. Therefore one has to be cautious in deriving a general figure of the rate of brain injury.

treatment and monitoring tools. The description of each technology and the protocol for their use are detailed below.

### **b. Background**

This project proposes to use two novel technologies for treatment and the monitoring of therapy efficacy: rTMS and EVestG.

**Transcranial Magnetic Stimulation (TMS)** – TMS is a relatively new, but popular and well-tolerated, neuromodulation method that is emerging as a therapeutic tool for a variety of neurological conditions [1]. TMS is a noninvasive procedure based on the principles of electromagnetic induction, whereby a magnetic field pulse (generated by the coil placed on the scalp) produces electrical currents in underlying neural tissue of the brain. The repetitive application of TMS (rTMS) pulses can modulate cortical excitability, either increasing or decreasing it, even well beyond the duration of stimulation. This has shown to have therapeutic potentials for several neurodegenerative diseases, i.e. Parkinson, stroke and psychiatric disorders such as depression [25-26].

rTMS has been increasingly used and found to be a promising noninvasive treatment for an array of brain disorders such as depression (FDA approval in 2008), migraine (FDA approval for prophylaxis in 2008), post-traumatic stress disorder, obsessive-compulsive disorder, stroke, Parkinson's disease, Alzheimer's disease, and epilepsy, as well as tinnitus and a variety of pain syndromes [27-29]. There are several reports of case studies that show beneficial effects of rTMS treatment on patients with severe TBI [30-33]. Four clinical trials are currently in progress to examine the efficacy and safety of rTMS in the treatment of TBI [34]. It is proposed that potential targets of rTMS therapeutic application in TBI patients could be TBI-related symptoms and functional sequences [35]. A number of studies demonstrate that rTMS treatment improves cognitive functions (i.e. attention/concentration, memory, executive functions/working memory, learning, psychomotor speed, language, emotional processing, and global cognitive functioning) [36,37], gait [38], balance [39], symptoms of depression [40] and anxiety [41], tinnitus and auditory processing [42], visual acuity [43], sleep quality [44], motor function of upper and lower limb(s) [45,46], spasticity [47], and reduces fatigue [48]. The same pattern is likely to be translated to patients with above-named symptoms due to TBI.

The fundamental rationale for therapeutic use of rTMS is based on compelling evidence that rTMS is able to modulate long-term neural plasticity at the network level [39,49,50]. These lasting neuroplastic changes induced by rTMS would likely help promote the recovery of brain function and decrease the burden of disabling sequelae of TBI, based on the evidence that it helps slowing cognitive decline in Alzheimer's patients.

We are currently applying high-frequency (20 Hz) rTMS bilaterally over the dorsolateral prefrontal cortex (DLPFC) as treatment for Alzheimer's [51]. We envision using a similar protocol and same location of the brain for TBI treatment with rTMS, as four case studies [30-33] that applied rTMS to TBI patients, also applied it to DLPFC brain regions at the either 10 or 20 Hz frequency. The DLPFC plays an important role in cognitive (executive, attention, memory) function of the brain due to its interconnectedness with other brain regions. The DLPFC

coordinates function with the rest of the brain and also helps to shift between tasks, and therefore has a role in working memory [50].

In general, rTMS is considered to be a safe, non-invasive, painless and harmless procedure. Review papers on rTMS tolerability and safety when applied to populations with depression (and on pregnant women with depression), Parkinson's disease, Huntington's disease, epilepsy, and anxiety have reported mild discomforts including mild tension headache (due to stimulation of the peripheral muscles in the scalp) after the session that diminishes within a couple of hours and some mild annoyance during the stimulation. The induction of migraine by rTMS is rare, and indeed rTMS to the left DLPFC has been used to reduce migraine headache. rTMS at high frequencies increases the risk of seizure induction. Although the risk of seizure at frequencies lower than 30 Hz is very low, in our study, we exclude people with a history of seizure as well as those with large ischemic scars (as that also increases the risk of seizure induction).

**ElectroVestibulography (EVestG)** – EVestG [1] is a noninvasive technique to record neural activity from the vestibular apparatus and vestibular nuclei. EVestG signals are recorded from the external ear in response to a vestibular stimulus. They are the brain signals modulated by the vestibular response. The recorded signal is comprised of a series of acoustic and vestibular random and driven generated small field potentials from which the vestibular response can be separated. The vestibular response can be separated by taking measures when the vestibular system is at rest and when perturbed by passive whole body tilt [52]. EVestG signal analysis has shown great promise for diagnosis and separation of patients with depression [53], Parkinson's disease [54], schizophrenia [55], Meniere's disease [56], Attention Deficit Hyperactivity Disorder [57] from healthy controls. Pilot studies have shown EVestG to have sensitivities and specificities above 85% for a population of between 40 and 50 years of age.

TBI is commonly associated with vestibular dysfunction, and many survivors often experience persistent dizziness, imbalance, vertigo [16, 17]. Considering the well-known bidirectional anatomical links of the vestibular system (i.e., the vestibular nucleus is linked to the pre-frontal cortex path), EVestG signals are expected to change following TBI, and should be indicative of an injury. A recent pilot study conducted by our group has demonstrated that evaluation of vestibular performance using EVestG might be a useful measure of the physiological recovery state following mTBI (see Figure 1) [58]. Hence, physiological EVestG assessment may offer a great promise in evaluating treatment efficacy and monitoring of recovery after TBI.

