### **Research Plan and Methods**

The study will be performed as a pilot prospective, randomized, controlled, double blind, two parallel groups clinical trial (examining sham versus active treatment). At the end of the study, the active treatment will be offered to the Sham Group if the treatment is shown to be effective.

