### **Study Protocol**

#### **Study Population/Participants**

A total of 20 individuals with a clear diagnosis of TBI within the last 12 months (as confirmed by their treating Neurologist, Psychiatrist or Medical Rehab Physiatrist, who are the co-investigators in this study) prior to the commencement of this study will be recruited from Riverview Health Center patient and [name] clinic patient population. Ten patients will be randomly assigned to **Treatment Group** and 10 others to **Sham Group**. Neither the patients, nor the clinical assessors will know the sham versus real treatment group assignment. In addition, as one of the objectives of this study is to evaluate the EVestG assessment as a

diagnostic and monitoring tool, 20 age-and-gender-matched cognitively healthy volunteers will be recruited as controls for the EVestG assessment. The healthy **Control Group**'s participants must not have any history of TBI and also meet other exclusion criteria for patients group listed below.

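### No side-effect check is scheduled during the treatment weeks, and no adverse-event summary by arm is planned

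*Combined protocol and SAP*

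**What the plan says.** **Expected reactions.** Under b. Background, the plan reports from published reviews "mild tension headache (due to stimulation of the peripheral muscles in the scalp) after the session that diminishes within a couple of hours". It also mentions slight annoyance while the pulses are being given, and it calls induced migraine rare. On seizure it says "Although the risk of seizure at frequencies lower than 30 Hz is very low", and it excludes people with a seizure history or large ischemic scars.

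**Safety evidence.** The reviews are in depression, Parkinson's disease, Huntington's disease, epilepsy and anxiety. For TBI, the same section says "Four clinical trials are currently in progress to examine the efficacy and safety of rTMS in the treatment of TBI", and supports the choice of target with "four case studies [30-33] that applied rTMS to TBI patients, also applied it to DLPFC brain regions". It also cites two articles on noninvasive brain stimulation in TBI (references 35 and 50) and the team's own use of 20 Hz stimulation in Alzheimer's disease.

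**Session procedure.** rTMS Treatment Procedure fixes the trains, frequency, intensity, naming task and sham spacer. It requires a motor threshold before each session and states that the daily dose is within the safety limit.

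**Schedule.** Table 1 gives 5, 5 and 2 treatments in weeks 1, 2 and 3 and no assessment in those weeks. The patient battery falls at weeks 0, 4, 8 and 12.

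**Medical input.** TBI is confirmed by the treating Neurologist, "Psychiatrist or Medical Rehab Physiatrist, who are the co-investigators in this study". Medical collaborators assess symptoms, and Data analysis checks its algorithms against the referring physician's updated diagnoses.

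**After the trial.** At the end, "the active treatment will be offered to the Sham Group if the treatment is shown to be effective".

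**The concern.** The plan names reactions that it expects at or soon after a session, but schedules no question that would record them. A headache that has gone within hours leaves no trace at a visit one or more weeks later, and no analyst can recover it.

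Headache is also a persistent symptom of the condition itself. The Rationale lists "somatic and emotional symptoms (sleep disturbances, fatigue, headache and emotional changeability" among them. A headache mentioned in passing during week 2 could be a reaction to stimulation or the patient's usual state. The baseline RPQ gives a coarse reference, but not the level on the day, and only the same question asked in the sham arm allows a fair comparison.

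Two things are at stake:

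- A patient with a marked reaction may return for the next session, often the following day, without any required review.
- The decision to offer active rTMS to the Sham Group has a stated efficacy condition and no specified tolerability data beside it.

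**Working it through.** The plan states no figure on this point, so there is none to reproduce. The check is of the text, followed by arithmetic on exposure and on what a log could show.

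**1. Text check, Objectives to Table 1**

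| Place | Nearest provision | Asks about session reactions? |
|---|---|---|
| Objectives | Efficacy, EVestG and spatio-temporal measures | No |
| Exclusion Criteria | Entry exclusions, partly tied to a published TMS safety guideline; physician symptom assessment described around enrolment | No |
| rTMS Treatment Procedure | Motor threshold before each session, used to set intensity | No |
| Neuropsychological measures | RPQ, MoCA, MADRS and Stroop, four times | Not timed to sessions |
| Data analysis | MANOVA, correlation, discriminant analysis, clustering | No harms summary |
| Table 1, weeks 1-3 | No assessments | No |

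Objective 3 speaks of spatio-temporal assessments before and after treatment sessions. Table 1 places these at weeks 0, 4, 8 and 12. On either reading they measure performance, not side effects.

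**2. Exposure.** There are 10 patients per arm (Study Population). The session count is 12 in Table 1 and 13 in the treatment text. That mismatch is a separate matter, and both counts are carried here.

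- Active arm: 10 × 12 = 120, or 10 × 13 = 130 sessions.
- Both arms: 20 × 12 = 240, or 20 × 13 = 260 sessions.

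**3. Time for a review.** With 5 + 5 + 2 sessions there are 11 gaps: 4 + 4 = 8 of one day, 2 across a weekend and 1 of two days. With 13 sessions there are 12 gaps, at least 8 of one day.

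**4. What a log could show in 10 active patients.** The event rates are assumptions; the documents give none.

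- No patient affected: the one-sided 95% upper bound is 1 − 0.05^(1/10) = 0.259, or 25.9%.
- Two of 10 affected: the Clopper-Pearson 95% interval is 2.5% to 55.6%.
- Chance of seeing at least one affected patient, 1 − (1 − p)^10:

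| Assumed true rate p | Calculation | Chance |
|---|---|---|
| 20% | 1 − 0.80^10 | 89% |
| 10% | 1 − 0.90^10 | 65% |
| 1% | 1 − 0.99^10 | 9.6% |

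A reaction that affects one patient in five would very probably appear in the log. A reaction at 1% probably would not.

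**The case against.** The strongest case is that this is a 20-patient pilot in which tolerability is not an objective, and no stated conclusion depends on it. Staff see each patient at every session of about 20 minutes, so spontaneous reports are possible, and a seizure during a session would be noticed without a form. Entry exclusions, the threshold measurement and physician co-investigators are real safeguards. Ten patients per arm cannot establish safety. Repeated questions could also lead patients to guess their arm or colour later RPQ answers.

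Most of this stands, and it limits the size of the point. It does not remove it: spontaneous reports are not systematic, and none of the safeguards is tied to reactions at a session.

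Some stronger readings are tempting, but the documents do not support them:

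- *The trial will produce no tolerability data, or has no safety monitoring.* The title and consent pages are not in the public file and may deal with side effects. The point is confined to the sections supplied.
- *A headache during treatment could never be interpreted.* The baseline RPQ gives both arms a coarse reference, and the four-visit battery can show lasting worsening.
- *The Sham Group will be offered rTMS regardless of tolerability.* The plan states an efficacy condition. It does not say that other considerations will be ignored.
- *The plan has almost no basis in TBI.* It cites two further articles on brain stimulation in TBI beyond the case studies. Their contents cannot be seen here, and neither is cited for session monitoring.

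**Conclusion.** The point holds, as a minor one. In the sections supplied, no side-effect check is scheduled in the treatment weeks, no review of reactions is required before the next session, and no adverse-event summary by arm is planned, although the Background section names the reactions to expect. Because those reactions are short-lived, the omission affects what the trial collects and cannot be repaired at analysis.

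The size is 120 to 130 active sessions (240 to 260 in both arms) with no required question at any of them. No harm is alleged, and no efficacy or EVestG result is affected. A log would describe common, mostly mild reactions and say little about rare ones. The conclusion assumes that the pages not supplied contain no such procedure.

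**What to change.** **Table 1, weeks 1-3.** Add one short scripted side-effect log per session, worded identically in both arms. At arrival, ask for current headache and anything since the last session. At the end, ask for headache and discomfort. The patient should complete it where possible, because the person fitting the wooden spacer may know the arm. Keep it from the assessors, since the plan promises "Neither the patients, nor the clinical assessors will know the sham versus real treatment group assignment".

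**rTMS Treatment Procedure.** Require any seizure, new migraine or marked worsening to be referred to an existing study physician before that patient's next session, without disclosing the arm. No dedicated extra physician is needed, and no separate questioner at weeks 4, 8 and 12.

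**Data analysis.** State that counts per patient will be reported by arm, descriptively and without a test, and considered with the efficacy result before active rTMS is offered to the Sham Group.

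**Cost.** Assuming 2 to 3 minutes per session for the whole log, 240 × 2 min = 8 hours and 260 × 3 min = 13 hours, plus data entry and occasional physician time. No extra visit is needed. A small risk remains that repeated questions or logged sensations hint at the arm to patients or staff. Identical wording in both arms and keeping the log from assessors limit that risk but do not remove it.

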### **Exclusion Criteria for all Participants**

- 1) Use of neuro- or psycho-active medications as published in recommendations [26]
- 2) Active use of illicit drugs
- 3) History of epilepsy
- 4) History of any other brain lesions including tumors, infectious, vascular, or metabolic lesions
- 5) Severe or recent heart diseases
- 6) Alcoholism
- 7) Pregnancy
- 8) The presence of metallic objects in the body; dental implants are fine but people with pacemakers are to be excluded; anything that is unsafe under MRI would be considered unsafe for TMS [26].
- 9) Lack of ability to adequately communicate (understand, read, speak) in English and understand the experimental protocol.
- 10) Pending litigation (i.e., patients with pending actions regarding disability reports, litigation, or other kinds of financial compensation).

Participants will receive the details of the study, and be asked to sign a written consent form prior to experiments. Upon meeting the eligibility criteria and providing informed consent, each patient participant will be randomly assigned to either treatment or sham groups; this assignment will not be revealed to the patients until the end of study. *The Sham Group's participants will be offered a course of treatment after the study is finished if the results show improvement beyond the placebo for the participants in Treatment Group.* Patients will be thoroughly assessed by the medical collaborators for their symptoms, and localization of the damage to the brain. The cognitively healthy Control Group will not receive any rTMS treatment. All participants will complete a series of cognitive and mental assessments, and EVestG assessments. The Control Group will go through a lesser number of questionnaires as there is no need for run concussion severity assessment on control group. The details of the study procedure are described below, and Table 1 summarizes the study protocol.

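### The safety text excludes anyone with a history of seizure, but the exclusion list that governs randomisation names only epilepsy

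*Combined protocol and SAP*

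**What the plan says.** The Introduction (b. Background) gives the safety reasoning for rTMS. It states that "rTMS at high frequencies increases the risk of seizure induction". It describes the risk below 30 Hz as very low, and still adopts a precaution for this study: "we exclude people with a history of seizure as well as those with large ischemic scars".

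The formal rules come later, in Exclusion Criteria for all Participants. Three of the ten items bear on this point:

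- Item 1: "Use of neuro- or psycho-active medications as published in recommendations", with a citation to the TMS safety guideline (reference 26).
- Item 3: "History of epilepsy", with no citation.
- Item 4: "History of any other brain lesions including tumors, infectious, vascular, or metabolic lesions".

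The same section makes these rules the gate to the trial: "Upon meeting the eligibility criteria and providing informed consent, each patient participant will be randomly assigned to either treatment or sham groups". It also describes a medical assessment: "Patients will be thoroughly assessed by the medical collaborators for their symptoms, and localization of the damage to the brain". Under rTMS Treatment Procedure, the stimulation frequency is 20 Hz.

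**The concern.** A history of seizure is a wider category than a history of epilepsy, because a person can have had a seizure without ever being diagnosed with epilepsy. A single seizure after the head injury is one example; it is mine, as the protocol does not mention it. If screening is done from the numbered list, as the randomisation sentence invites, such a person passes item 3 although the background text says the study excludes them.

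What is at stake is safety. The mismatch concerns the one adverse event for which the protocol sets out its own exclusion rule, in a trial where every patient has had a brain injury and half are assigned to active stimulation. The same list also stands behind the later offer of active treatment to the Sham Group (Research Plan and Methods), and the supplied text describes no fresh eligibility check at that point.

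**Working it through.** No arithmetic model applies. The check compares the two texts and then looks for anything else that would close the gap.

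**1. Are the two terms used as synonyms?** Nothing in the protocol defines one as the other. The background section uses epilepsy as the name of a patient population in earlier tolerability reviews: "epilepsy, and anxiety have reported mild discomforts including mild tension headache". It then uses a different term, history of seizure, for this study's own exclusion. Earlier in the same section, epilepsy appears in a list of disorders treated with rTMS, again as a diagnosis.

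**2. Where does the protocol mention seizure?** The word occurs 4 times in the supplied text, all in the safety paragraph of b. Background. Of the 10 exclusion items, 0 name seizure and 1 (item 3) names epilepsy.

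**3. A test case.** Take a patient with a qualifying TBI and persistent symptoms, a prior seizure, no epilepsy diagnosis, no anti-seizure drug or other medication caught by item 1, and none of the other listed conditions.

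| Text | Does it exclude this patient? |
|---|---|
| b. Background, safety statement | Yes |
| Item 1, medications | No. It may catch a patient treated for seizures, but this one is untreated |
| Item 3, epilepsy | No, there is no such diagnosis |
| Item 4, other brain lesions | No. It covers the ischemic-scar half of the background sentence; a seizure is not a lesion |
| Items 2 and 5 to 10 (illicit drugs, heart disease, alcoholism, pregnancy, metal, English, litigation) | No, they concern other matters |

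The same patient is therefore excluded by one part of the protocol and eligible under the other.

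**4. Does a physician check close the gap?** Under Inclusion Criteria for Patients, physicians confirm the persistent TBI symptoms. The assessment described after the exclusion list covers symptoms and the site of damage. Neither mentions seizure history.

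**5. Does a citation import a wider definition?** Items 1 and 8 refer to the TMS safety guideline. Item 3 does not.

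**6. How many patients does the criterion govern?** Ten are randomised to active treatment, and up to 10 Sham Group patients may be offered it afterwards: 10 + 10 = 20 at most. This is the number whose access to active rTMS depends on the list. It is not an estimate of how many have had a seizure.

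**The case against.** The strongest reply is that the safeguard is already written down. The background statement is current text in the same document, and a reader who takes the protocol as a whole would apply the stricter rule. That is correct, and it is why this is an inconsistency and not a missing protection. It does not remove the problem, because the randomisation sentence points to the eligibility criteria, and a safety exclusion should not depend on the screener recalling a background paragraph.

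A second reply is that the background sentence is only a loose paraphrase of the list: it also says ischemic scars where item 4 says vascular lesions. The comparison does not carry over. Vascular lesions include ischemic scars, so there the list is at least as broad as the prose. With seizure and epilepsy the list is narrower, and the two texts still give different answers for the same person.

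Third, the treating specialists are co-investigators who confirm the diagnosis (Study Population/Participants), so an oversight is less likely. That is fair, but no seizure enquiry is among the tasks described for them.

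Finally, the protocol calls the risk below 30 Hz very low, and the number of affected candidates is unknown. Both points stand, and they limit what can be claimed. But the protocol adopts the exclusion despite the low risk, so the judgment has already been made and the list should carry it out.

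**Conclusion.** The concern holds and should be fixed. The exclusion list is narrower than the safety rule the protocol states for itself, and no other listed item or described check reaches an untreated prior seizure without an epilepsy diagnosis. Confidence is high for the mismatch in the text.

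The practical consequence cannot be sized. The documents give no rate of prior seizure without epilepsy and no seizure rate under rTMS, so no probability of wrongful enrolment or of harm is claimed. The gap opens only if screening uses the list without the background text. How far item 1 narrows it depends on the cited guideline, which was not available. Consent and title pages were not part of the reviewed text, so the statement that nothing else screens for seizure applies to the supplied text only. No analysis or sample-size result is affected.

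**What to change.** Reword exclusion item 3 as *History of seizure or epilepsy*, and leave the statement in b. Background unchanged. The mismatch should not be resolved the other way, by narrowing the safety statement to epilepsy.

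The cost is a one-line wording change. Some patients with a prior seizure become ineligible, so recruiting 20 patients may be slightly slower. Because the list applies to all participants, healthy controls with a prior seizure would also be excluded although they receive no rTMS; item 3 already applies to them in its narrower form.
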